The goal of the present study is to establish whether delayed discounting is engaged in a WLM intervention that involves EFT, whether this engagement mediates adherence to PA recommendations, and whether environmental factors moderate this relationship. We will do this by testing TST-based mediational pathways in both a standard WLM intervention (Weight Loss Maintenance- Healthy Thinking: WLM-HT) and a

WLM intervention that explicitly seeks to engage DD through EFT (Weight Loss Maintenance+ Future Thinking: WLM+FT). Given that the stated focus of many WLM interventions is on selfregulation^{14,18} and the data linking DD to eating and exercise behaviors^{29,40}, it is reasonable to propose that this putative target is engaged in standard WLM interventions, although this hypothesis has not yet been empirically tested. At the same time, we recognize that there is tremendous variability in response to WLM interventions⁶, which suggests the need to more systematically engage putative targets such as DD to improve behavioral adherence and long-term outcomes. EFT is a promising strategy but has yet to be explored in WLM. Thus, testing of the DD mediational pathway within these two interventions will allow for both within- group examinations of the hypothesized mechanism of action as well as between-group comparisons of whether explicit engagement of DD results in greater behavioral adherence and improved WLM outcomes. It is hypothesized that 1) Compared to WLM-HT, WLM+FT will produce more engagement of DD and PA adherence as measured by EMA and accelerometry. 2) In both WLM-HT and WLM+FT, within-person mediational pathways will be found between participation in the intervention and PA and changes in delayed discounting on 2a) a daily basis (EMA) and 2b) over longer-time periods (1- and 3-month change predicting PA outcomes at 6 months). 3) Environmental context will moderate the mediational pathways in both interventions such that DD will be a stronger determinant of behavior in environments with more proximal costs than in environments with more proximal benefits.

Design, Procedures, Materials, and Methods.

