Power. Based on prior DD and EFT work^{31,34,39}, power is computed for an effect size (d) of 0.50. The computations assume an intraclass correlation (ICC) of 0.250 for the 4 time points clustered within each participant. The standard deviation is assumed to be the same in the two conditions. The criterion for significance (alpha) has been set at 0.05. The test is 2-tailed, which means that an effect in either direction will be interpreted. Given these assumptions, the study will have 82.1% power to yield a statistically significant result that will increase in one unit per number of individual covariate(s) included in the models. Accounting for 15% attrition, 15 more participants will be added, so a total of 160 participants will be enrolled in Phase I.

Analyses.

Primary hypothesis 1: WLM+FT will produce more engagement of DD and PA adherence. Descriptive statistics will be generated on all the demographic variables as well as mediators (DD), moderators

(environmental variables), covariates (WAIS-II) and outcomes (PA and weight). Differences between WLM-HT and WLM+FT will be assessed through chi-square tests (proportions) or Student's t-test (means) at each time point; if differences on any of the demographics are found at baseline, the variable will be used as a covariate in the main model. The main outcome, PA distribution data will be examined and if variables violate distributional assumptions of normality, will be analyzed using generalized linear model (GLM) procedures, which enable the use of non-Gaussian error models. Using a mixed-effects model in Mplus we will be able to estimate the main effect of the intervention considering the four time points nested within individuals allowing for time-varying effects of covariates to vary with time for the daily data collected.

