Primary hypothesis 2: Within-person mediational pathways will be found between participation in the intervention and PA and changes in DD on 2a) a daily basis (EMA) and 2b) over longer-time periods (1- and 2month change predicting PA outcomes at 4 months). Using mixed-effects mediation modeling assuming time points clustered within individuals with Mplus and mediation package from R[104-107], we will test how the relationship between intervention condition and PA is mediated by change in DD over time by using daily data and also running prediction models by the four time points. DD will be evaluated for normality and linearity assumptions and if assumptions are violated, GLM models will be established to determine the indirect effect.

Exploratory hypothesis: Environmental context will moderate the mediational pathways such that DD will be a stronger determinant of behavior in environments with more proximal costs. A moderated mediation mixedeffects model will test the strength or weakness of the indirect effect and/or the direct effect of the intervention condition on PA by the different environmental factors measured. The mixed-effects will consider effects by the daily data collected within the four general time points nested within individuals.

Missing data. We will run a systematic analysis of missing EMA data to determine whether the likelihood of response at any given prompt is time-varying (e.g., time of day/week, activity level). We anticipate approximately ~80% of prompts will be answered⁷⁵. If needed, we will use multilevel data imputation strategies ⁹⁴. For clinicbased data, type of missingness will be evaluated and values will be imputed using full information or restricted maximum likelihood estimation ⁹⁵. All variables in our models will be used to impute missing data. Sensitivity analyses will be used to compare results with and without imputed values.

Inclusion/Exclusion Criteria.

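### Primary hypothesis 2 is stated for both arms, but its specified mediation test is a between-arm indirect effect that cannot show whether the pathway holds in WLM-HT

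*Combined protocol and SAP*

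**What the plan says.** The last paragraph of Purpose / Introduction states hypothesis 2 by arm: "In both WLM-HT and WLM+FT, within-person mediational pathways will be found between participation in the intervention and PA". The same paragraph says that testing the pathway in the two interventions "will allow for both within- group examinations of the hypothesized mechanism of action as well as between-group comparisons". On the comparator it says "it is reasonable to propose that this putative target is engaged in standard WLM interventions, although this hypothesis has not yet been empirically tested", so DD engagement in WLM-HT is one of the trial's own questions. Its timing for 2b is "1- and 3-month change predicting PA outcomes at 6 months".

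Under Analyses, Primary hypothesis 2 is restated without naming the arms: "Within-person mediational pathways will be found between participation in the intervention and PA and changes in DD on 2a) a daily basis (EMA". The months for 2b are now 1 and 2, predicting PA at 4. This agrees with Phase II Assessments, which places visits at baseline and 1, 2 and 4 months. The test is a mixed-effects mediation model: "we will test how the relationship between intervention condition and PA is mediated by change in DD over time by using daily data", together with "running prediction models by the four time points".

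Two other parts of Analyses touch on DD. Primary hypothesis 1 provides summaries ("Descriptive statistics will be generated on all the demographic variables as well as mediators (DD), moderators"), arm comparisons at each visit and a main effect of intervention. The exploratory hypothesis adds a moderated mediation, but its moderators are environmental factors and the effect concerned is again that of intervention condition.

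**The concern.** Intervention condition does not vary within a person. A mediation model with condition as the exposure therefore asks whether the arms differ in DD change and whether that difference carries through to PA. Hypothesis 2, as the introduction words it, asks whether the pathway operates in each arm. The two questions can have different answers.

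If both programmes lower DD equally and DD drives PA in both, the introduction's hypothesis is true and the specified indirect effect is zero. If only WLM+FT lowers DD, the claim fails for WLM-HT and the specified indirect effect is not zero. No by-arm estimate of DD change or of the DD-to-PA path, no DD-by-condition term and no rule for judging both arms is given. The promised within-group examination of WLM-HT thus has no specified inference.

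**Working it through.** **1. The plan's own figure.** Inputs from Power and the design overview: d = 0.50, ICC 0.25, 4 time points, two-sided alpha 0.05, 70 randomised, 15% attrition. Equal allocation is assumed, since no ratio is stated.
- Per arm: 70 × 0.85 / 2 = 29.75, about 30.
- Design effect: 1 + (4 − 1) × 0.25 = 1.75.
- Noncentrality: 0.50 / √(2 × 1.75 / (4 × 30)) = 0.50 / 0.171 = 2.93.
- Power from the noncentral t with 58 df: 82.09%.

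The stated 82.1% reproduces. It describes a between-arm contrast, and Power gives nothing for a within-arm or mediation effect.

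**2. What the specified test estimates.** In a linear model with a common slope b, let d(HT) and d(FT) be the mean changes in DD. Then

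indirect effect = [d(FT) − d(HT)] × b.

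The documents give neither the DD falls nor b, so the values below are assumptions in SD units.

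| DD fall, HT / FT | Engaged in both arms? | b = −0.1 | b = −0.2 | b = −0.3 | b = −0.4 |
|---|---|---|---|---|---|
| 0.5 / 0.5 | yes | 0 | 0 | 0 | 0 |
| 0 / 0.5 | not in WLM-HT | 0.05 | 0.10 | 0.15 | 0.20 |
| 0.5 / 1.0 | yes | 0.05 | 0.10 | 0.15 | 0.20 |

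The last two rows are identical, for example (−0.5 − 0) × (−0.2) = (−1.0 + 0.5) × (−0.2) = 0.10. This is a property of the estimand, so a larger sample would not change it.

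**3. Illustration by simulation.** A simplified model was used: one DD change per person, 30 per arm, joint-significance test, 4000 runs, assumed effects with DD change in units of its own SD. With equal DD change of 0.5 and slope 0.5 in both arms, the between-arm test was significant in 4.8% of runs; by-arm tests found the pathway in about 54% of runs in each arm. With no DD change and no DD-to-PA path in WLM-HT, and change 1.0 with slope 0.6 in WLM+FT, the between-arm test was significant in 55% of runs. These are not error rates for this trial.

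**4. Precision of by-arm estimates.** Take n = 30, total SD 1 and t(29) = 2.045. The SD of change is √((1 − ICC) × 4/3) for the mean of three follow-up visits minus baseline, and √((1 − ICC) × 2) for one visit. Power does not say which variable its ICC describes, so 0.5 and 0.7 are added as an assumed range.

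| ICC | Half-width, mean of three visits | Half-width, single visit |
|---|---|---|
| 0.25 | 2.045 × 1.00 / √30 = 0.373 | 2.045 × 1.225 / √30 = 0.457 |
| 0.5 | 0.305 | 0.373 |
| 0.7 | 0.236 | 0.289 |

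At ICC 0.25, power for an assumed 0.5 SD fall within one arm is 75% (mean of three) or 58% (single visit).

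For 2b, 4-month PA was regressed on DD change by condition with baseline PA adjusted (60 people, simulated). The half-width of each arm's slope is about 0.30 with one month's change entered and 0.36 with both, at ICC 0.25. At ICC 0.7 these become 0.35 and 0.42.

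**5. Lack of an untreated control.** An assumed drift of 0.2 to 0.3 SD with no treatment effect would be declared a DD decline in 18% to 36% of trials (mean of three visits) or 14% to 25% (single visit), at ICC 0.25.

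**The case against.** The strongest reply is that the both-arms wording sits only in the introduction, and that paragraph is at least partly out of step with the rest: its months 1, 3 and 6 do not fit the 0, 1, 2 and 4 schedule. Analyses has the current months and does not repeat the both-arms claim. This has force. But the introduction uses the current arm names and stands in the same document, so its status is unclear and the sponsor has to settle it.

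A reader might infer that hypothesis and test conflict even on the Analyses wording alone, because it says within-person while condition is fixed. The documents do not support that. Within-person is not the same as within each arm, and a mixed model with time points clustered in individuals can carry a within-person DD-to-PA path. On that wording, what is lacking is mainly how daily DD is coded and centred.

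A reader might also infer that the trial will mis-decide a primary hypothesis. That goes too far as well. No rule turns the between-arm indirect effect into a verdict on WLM-HT, and the equal-engagement case also requires the DD part of hypothesis 1 to be false.

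Finally, by-arm estimates are weak and uncontrolled, so they should not become the criterion. Suppose both arms were taken to mean that all four by-arm intervals exclude zero. With 0.5 SD falls in both arms and ICC 0.25, a true hypothesis would then be supported in about 0.2% of simulated trials at a slope of −0.1 and 27% at −0.4. That part of the objection stands and shapes the fix.

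The time-point prediction models may include a DD-to-PA term, but they are described by time and not by arm, so they do not close the gap.

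**Conclusion.** The concern holds against hypothesis 2 as the introduction states it. The only mediation test specified for that hypothesis has a between-arm estimand: zero under equal engagement, and equal for DD falls of 0/0.5 and 0.5/1.0 SD. It cannot show whether the pathway holds in WLM-HT. This rests on a linear model with a common slope; the falls and slopes are assumed for illustration.

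If the introduction's both-arms claim is superseded, the mismatch shrinks to wording and to the coding of daily DD. Hypothesis 1 and the 82.1% power figure are not affected. The point should be fixed because it concerns a primary hypothesis and the data needed are already being collected.

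**What to change.** Under Analyses, Primary hypothesis 2:

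- **Label the existing test.** Keep condition to DD change to PA, call it the between-arm mechanism test, and say that it is not evidence for the pathway within each arm.
- **Add by-arm estimates with 95% confidence intervals.** Give DD change from baseline and the DD-to-PA path in each arm, using a DD change by condition term with time in the model and baseline PA adjusted. For 2b, use 1- and 2-month DD change to predict 4-month PA. Report these as supportive and associational, because there is no untreated control, and do not use them as a pass/fail criterion.
- **Separate two quantities for 2a.** Use change from the month-0 EMA wave for DD engagement. Use person-mean-centred DD, measured before the PA it predicts, for the within-person DD-to-PA path.
- **Reconcile Purpose / Introduction with Analyses** on the both-arms claim and on the months. If the claim is no longer intended, restate hypothesis 2 as between-arm.

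The cost is SAP wording and a few model terms, with no new data. The drawback is imprecision at about 30 per arm, as calculated above: at ICC 0.25, about 0.37 SD either side for mean DD change over three visits and 0.46 SD for a single visit. Precision for the daily EMA analysis in 2a was not calculated and could differ.

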Participants in this study will be 160 healthy overweight or obese men and women ages 18-70 recruited from the greater Hartford, Connecticut area. Participants will have a body mass index between 30 and 50 kg/m². This weight criterion was chosen because of the high prevalence of overweight and obesity in the United States and because of the health implications associated with obesity. We have chosen a BMI upper limit of 50 kg/m², as individuals with a BMI greater than 50 have more medical co-morbidities and require greater medical supervision and eligibility screening. Additionally, as the EMA protocol will require answering questions on a smartphone app several times a day, participants must have a smartphone and use text and/or email on a daily basis to be eligible.

Participants will be excluded if they report being unwilling to complete accelerometry or EMA protocols, are unable to walk 2 blocks without stopping; are currently participating in a weight loss program, taking a weight loss medication, have a history of bariatric surgery, or lost ≥ 5% of body weight during the past 6-months; are pregnant, lactating, less than 6 months post-partum, or plan to become pregnant during the time frame of the investigation; report a medical condition that would affect the safety and/or efficacy of a weight management program involving diet and physical activity (e.g., uncontrolled heart problem); have a history of Multiple Sclerosis, traumatic brain injury or other neurological disorders; or report conditions that in the judgment of the Principal Investigator (PI) would render them potentially unlikely to be able to follow the protocol for 9 months, including terminal illness, plans to relocate, substance abuse, dementia, bulimia nervosa, or other significant psychiatric problems. Participants taking prescription medications, reporting joint problems, heart disease, or other medical conditions that are affected by weight loss or may limit their ability to exercise will be required to obtain written approval to participate in a weight loss program from their physician. During times of national emergency (e.g., COVID-19), participants unable or unwilling to engage in videoconference meetings will be excluded. Participants may be removed from the study by the PI if they are consistently (i.e. across several group

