meetings) disruptive or inappropriate during group interventions and have not changed their behavior after verbal and written feedback from study personnel. Participants may also be removed from the study if one of the conditions above (or other serious medical condition) emerges during the program and the participant's physician advises against continued participation.

Risks and Inconveniences.

The risks associated with this study are considered to be minimal and detailed below.

Intervention risks. The intervention involves a reduced calorie diet. The prescribed diet is balanced, with approximately only 1000 kcal per day deficit from the participant's usual intake, thereby minimizing risk. The physical activity recommendation is for moderate-intense activities. A potential risk is that participants become injured while doing physical activity; to minimize this risk, participants will be instructed to engage in brisk walking and gradually increase their activity over time. Participants may try unhealthy dietary or physical activity practices to lose weight. However, this is not common in adult behavioral weight loss programs; yet, to be cautious, participants' weight and self-monitoring information will be monitored by intervention staff and, if participants are losing weight too quickly (i.e. more than 10 pounds in a week) or there is suspicion of unhealthy practices (i.e. reporting under 800 calories per day average or over 1200 minutes physical activity a week), an interventionist will call and speak with the participant and make a referral, if necessary.

Assessment risks. Participants may also become uncomfortable when completing questionnaires; if this occurs, participants will be informed that they do not have to answer any questions that they are not comfortable answering. Another potential risk is that participants may not lose weight in the program. However, this is a potential risk in any weight loss program. Alternative treatments for overweight and obesity include diets with lower daily calorie recommendations, pharmacological interventions, and surgical procedures. These treatments are considered to have greater risks than the diet and activity program prescribed in this intervention. We do not anticipate any risks associated with the waist-worn activity monitor.

Benefits.

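### For clinic outcomes, the planned comparison with and without imputation cannot show bias from dropout that depends on unseen activity, and the removal rules provide for no later outcome assessment

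*Combined protocol and SAP*

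**What the plan says.** The Missing data paragraph says of clinic-based data that "type of missingness will be evaluated" and that "values will be imputed using full information or restricted maximum likelihood estimation". For EMA data it plans an analysis of non-response to prompts and, if needed, multilevel imputation. It closes with the only sensitivity analysis in the plan: "Sensitivity analyses will be used to compare results with and without imputed values".

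Inclusion/Exclusion Criteria contains two removal rules. On conduct: "Participants may be removed from the study by the PI if they are consistently" disruptive over several group meetings and have not changed after verbal and written feedback. On health: "Participants may also be removed from the study if one of the conditions above (or other serious medical condition) emerges during the program", provided the participant's physician advises against continuing. The conditions listed in that section include being unable to walk a short distance ("are unable to walk 2 blocks without stopping"). Group meetings belong to Phase II, so both rules reach randomised participants.

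No section says whether outcomes are collected after removal, and none defines an analysis set of all randomised participants. The paragraph on missed visits and dropouts covers make-up sessions and retention only.

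**The concern.** Likelihood methods such as FIML and REML fit the observed data directly. They fill in no values, so for the clinic outcomes there is nothing to take out again. The natural substitute sets complete cases, which need data missing completely at random, against the likelihood fit, which needs data missing at random. Both fail if loss depends on activity that nobody recorded, so their agreement is no evidence that either is right.

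This matters because the primary outcome is physical activity. Someone who leaves because of a new condition may well be less active afterwards than earlier readings predict. Removal from the study, as opposed to removal from sessions, can turn such a person into missing data. If this happens more in one arm, the between-arm comparison is biased and the planned check could look reassuring.

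**Working it through.** **Inputs from the documents.** Power paragraph: d = 0.50, ICC 0.25, 4 time points, two-sided alpha 0.05, power 82.1%, attrition 15%. Overview: 70 randomised; past retention 90-98%, that is 2-10% loss. Purpose/Introduction: SD 174.6 minutes, from the team's unpublished 6-month data.

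**Assumptions.** 1:1 allocation (35 per arm); the 15% applies to Phase II outcomes; SD 174.6 applies to weekly accelerometer MVPA; all loss occurs before month 1; the shortfall is in one arm only.

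**1. Reproduce the plan's power.** SD of a four-visit mean = sqrt((1 + 3 x 0.25)/4) = 0.661. With 30 per arm the noncentral t gives 82.1%. With 35 per arm it gives 87.6%. The stated figure therefore matches about 60 analysed, close to 70 x 0.85 = 59.5. The plan does not state this N; it is inferred.

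**2. Standard errors on that basis (30 per arm).**
- Four-visit mean: 174.6 x 0.661 x sqrt(2/30) = 29.8 min/week.
- Month 4 alone: 174.6 x sqrt(2/30) = 45.1 min/week.

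**3. Bias.** At one visit, bias = loss x shortfall. Baseline is complete for everyone randomised (Randomization section), so on the four-visit mean the bias is 3/4 of that. Type I error = P(|Z + bias/SE| > 1.96).

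| Loss | Shortfall | Contrast | Bias (min/week) | Bias/SE | Type I error |
|---|---|---|---|---|---|
| 15% | 0.5 SD | Four-visit mean | 0.15 x 87.3 x 3/4 = 9.8 | 0.33 | 6.3% |
| 15% | 0.5 SD | Month 4 | 0.15 x 87.3 = 13.1 | 0.29 | 6.0% |
| 10% | 0.5 SD | Four-visit mean | 0.10 x 87.3 x 3/4 = 6.5 | 0.22 | 5.6% |
| 2% | 0.5 SD | Four-visit mean | 0.02 x 87.3 x 3/4 = 1.3 | 0.04 | 5.0% |

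Here 87.3 = 0.5 x 174.6, which is also the d = 0.50 effect in minutes. The SE is held at 29.8 for the 2% and 10% rows. The month-4 bias of 13.1 is 15% of the target effect; the four-visit bias of 9.8 is 11%.

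**4. Would the planned check notice?** This was examined in a very large simulated sample: ICC 0.25, true effect 0.50 SD, about 15% dropout per arm after month 1, month-4 contrast. The mechanism acts in the WLM+FT arm only; dropout in the other arm is random.

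| Dropout in WLM+FT depends on | Without imputation | Likelihood | Truth |
|---|---|---|---|
| Nothing | 0.50 | 0.50 | 0.50 |
| Observed month-1 value | 0.54 | 0.50 | 0.50 |
| Unseen month-4 value | 0.65 | 0.64 | 0.50 |

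In the second row the comparison shows a gap, but the likelihood result is already right. In the third, the two results differ by about 0.01 SD while both are wrong by 0.14-0.15 SD. That mechanism was chosen to test the check. It is stronger than the 0.5 SD shortfall in step 3 and is not a forecast.

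**The case against.** **The plan looks at missingness in other ways.** A reader might infer that the quoted sentence is the only check. It is not: type of missingness is to be evaluated for clinic data and prompt non-response examined for EMA data. It is the only sensitivity analysis. The other checks rest on observed data and cannot separate missing at random from missing not at random.

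**EMA data may really be imputed.** With-versus-without has a meaning there, so the point about definition is confined to clinic outcomes.

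**The removal rules are narrow.** It would be tempting to say that an unblinded PI can remove people at will. The documents do not support that. Medical removal depends on the physician's advice, conduct removal needs disruption that persists after written feedback in a programme of seven group sessions, and the PI's blinding is not stated. Removals are probably few.

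**Loss of later outcomes is inferred from silence.** The text does not say that assessments stop after removal, nor that data already collected are discarded.

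**The size depends on the inputs.** The Power paragraph ties the 15% to Phase I enrolment. The SD comes from other, unpublished data and is not said to be accelerometer-based. Equal loss and equal shortfall in both arms would give no bias in the difference. If only month 4 were missing, the four-visit bias would be 13.1/4 = 3.3 min/week.

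All of this stands, and it limits the size of the problem. It does not make the planned comparison informative about dropout that depends on unseen activity.

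**Conclusion.** The point holds for clinic outcomes. The one sensitivity analysis is ill-defined under FIML/REML, and on its nearest workable reading it cannot detect the kind of dropout that would bias the primary analysis. The removal rules may add such dropout because they make no provision for later assessment.

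Bias is possible rather than shown, and modest under the stated assumptions: type I error of about 6% at 15% loss with a one-sided 0.5 SD shortfall, and 5.0-5.6% at the team's historical retention. A reader might reach about 7% by dividing the single-visit bias of 13.1 by the four-visit SE of 29.8. That pairs two different contrasts and should not be used.

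This is a cheap improvement that should be made. It does not show that the trial's comparison is unsound.

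**What to change.** 1. State that the likelihood-based mixed model is the primary analysis and includes all randomised participants in the arm to which they were randomised.
2. For clinic outcomes, replace the with/without comparison by delta-adjusted multiple imputation, with the adjustment varied separately by arm. For example, lower imputed MVPA by 0, 0.25 and 0.5 SD, and shift imputed delay discounting, on its analysis scale, toward steeper discounting. Report where the conclusion changes. The zero-shift case gives the missing-at-random reference.
3. In Inclusion/Exclusion Criteria, distinguish removal from intervention sessions from withdrawal from outcome assessment. The scheduled 1-, 2- and 4-month assessments would then continue with the participant's consent and where the participant's physician does not object. The decision to stop the intervention is unchanged.

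The cost is protocol and SAP wording, one extra analysis, and a few visits that are already scheduled. The third change has to be in place before removals occur, because outcomes not collected then cannot be recovered.
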